3.2 Analysis Populations

The analysis populations are defined in [Table 2](#).

Table 2: Analysis Populations

Population	Description
Enrolled	All subjects who sign the informed consent form.
Full Analysis Population	All subjects from cohorts 2 and 3 who are randomized and receive any study drug. Subjects are evaluated according to the treatment assigned at randomization. The Full Analysis Population will be used for all analyses of demographic baseline characteristics and efficacy data.
Per Protocol Population	A subset of the Full Analysis Population consisting of all subjects who receive the additional treatment with dapagliflozin post Week 12 and do not violate the terms of the protocol in a way that may affect the primary efficacy endpoint significantly (relevant protocol deviations (IPDs)). The relevant IPDs are reported in Section 3.3.2.
Safety Analysis Population	All subjects from cohorts 2 and 3 who are randomized and receive any study drug. Subjects are evaluated according to the actual treatment they received. The Safety Analysis set will be used for all safety analyses.
PK population	All subjects in the Full Analysis Population who have at least one detectable MEDI3506 serum concentration measurement post-treatment. The PK Analysis set will be used for all PK analyses.

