3.3.2 Important protocol deviations

Important protocol deviations (IPDs) are a subset of protocol deviations that may significantly impact the completeness, accuracy, and/or reliability of the study data or that may significantly affect a subject’s rights, safety, or wellbeing (ICH E3 guidance). The category of IPDs for the study are:

1. Informed consent
2. Study conduct/procedures
3. Investigational product
4. Safety
5. Other reasons

The relevant IPDs are those that have the potential to affect the results of the primary efficacy endpoint. Therefore, the category of relevant IPDs for the study would be:

- Did not meet inclusion/exclusion criteria
- Did received prohibited medication before end of treatment
- Missed visit (we allow 1 missed visit. For IA any missed Visit before Day 85 would be relevant PD, but not for the Final Analysis if they attend the rest
- Did not provide UACR samples / samples were lost / samples were damaged

Details of the IPDs will be provided in the protocol deviation plan (PDP), which will be developed for the study. The method for identifying IPDs will be documented in the PDP. All blinded IPDs will be agreed prior to study unblinding by blinded study personnel. Unblinding IPDs (i.e. those that relates to study medication/dosing and which could

potentially unblind a reviewer to subject's treatment group) will be agreed by unblinded personnel.

The number and percentage of participants with at least one IPD, including and excluding COVID-19 related IPDs, will be summarised following the IPD categories for each study intervention group and overall. A listing of all identified IPDs will also be provided. All issues reported due to COVID-19 pandemic, regardless of whether the type of issue is considered a protocol deviation or not, will be listed separately.

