3.4.1.2 Primary Efficacy Analyses

The primary efficacy endpoint of change from baseline in UACR at Day 169 (Week 24) for each of the MEDI3506 treatment groups compared with the pooled placebo group will be analyzed based on the Per Protocol Population. For the intercurrent events, if a subject is lost to follow-up (EOT), discontinues treatment due to AE, or uses prohibited medication, the UACR data are treated as missing on or after the event and no imputation is performed. The primary analysis will use a mixed model repeated measures (MMRM) analysis with a restricted maximum likelihood (REML) approach without multiplicity adjustment. UACR will be log-transformed before entering the data in the MMRM analysis to alleviate the skewness of the data. The model will adjust for fixed effects of treatment, visit, and treatment-by-visit interaction, randomization stratification factors, baseline log UACR and baseline log UACR-by-visit interaction. Randomization stratification factors are with SGLT2i background or not, in Japan or rest of world.

To allow generality for the covariance structure for the repeated measures, the variance-covariance matrix will be assumed to be unstructured, i.e., purely data dependent, to model within subject errors. If the unstructured variance-covariance matrix will not fit, i.e., fail to converge, the following covariance structures will be utilized in the order of 1) heterogeneous toeplitz, 2) heterogeneous autoregressive of order 1, and 3) heterogeneous compound symmetry. The first (co)variance structure which does not have a convergence problem will be the one used for the analysis. If a structured covariance has to be used, the “sandwich” estimator of the variance covariance matrix of the fixed effects parameters will be used in order to deal with possible model misspecification of the covariance matrix. The denominator degrees of freedom will be calculated according to the Kenward-Roger method. Additionally, there will be no adjustment for multiplicity.

If none of the above models converge, the analysis will be altered to use an analysis of covariance (ANCOVA) with last observation carried forward (LOCF) imputation method implemented. Details of this analysis is provided in the [Section 3.4.5](#) for sensitivity analysis.

Additionally, all collected values of UACR will be listed.

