3.4.1.2.1 Data Convention

Central laboratory urine samples for the determination of albumin and creatinine and calculation of UACR will be collected at the timepoints described in the schedule of study procedures in the protocol.

Participants will collect 1st morning void urine samples at home on 3 consecutive days (ideally day of visit and preceding 2 days [refrigerated overnight] which will be returned on the day of visit.

The UACR from each urine sample will be calculated as follows:

$$UACR (mg/mmol) = 10 \times \frac{Urine\ Albumin\ (mg/dL)}{Urine\ Creatinine\ (mmol/L)}$$

At each visit, the geometric mean of the triplicate UACR values will be computed and used for the analysis of UACR. In case of missing values for UACR the geometric mean will be calculated considering the number of the available measurements.

As UACR is assumed to follow a log-normal distribution, it will be log transformed for statistical analysis purposes obtaining the ratio of geometric means.

Percent change from baseline in UACR at $Visit_k$, k in $\{4, 5, 6, 7, 8, 9\}$ will be calculated as:

$$100 \times \left(\frac{GeoMean(UACR_{Visit_k})}{GeoMean(UACR_{Baseline})} - 1 \right)$$

If the urine albumin or urine creatinine lab result is below LOD (level of detection) or LOQ (limit of quantification), impute the missing value using half of the LOD or LOQ, prior to calculating the ratio.

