3.4.1.2.3 Missing Data Handling

In general, missing data will not be imputed.

In the primary MMRM model, all subjects and all data points up to the defined timepoint will be included. No subjects will be excluded because of missing data, and no imputation will be done for missing data.

For intercurrent events, if a subject is lost to follow-up (EOT), discontinues treatment due to AE, or uses prohibited medication, the UACR data on or after intercurrent day are treated as missing. Participants are expected to provide 1st morning void urine samples at home on 3 consecutive days. In case less than 3 values of UACR are available, the geometric mean will be calculated considering the number of the available measurements.

Baseline for UACR will be defined as the geometric mean of at-least 2 measurements of Day1(Visit 3) prior to the day 1 first dose of study treatment. Only samples collected prior to

the first dose of study medication will be used. If Day 1 visit (Visit 3) has less than 2 morning void measurements, and there are 1 or more measurements at Screening (Visit 2), then geometric mean of all morning void UACR measurements from both visits will be used as baseline. If there is only 1 measurement prior to the Day 1 first dose of study treatment (either Day 1 visit (Visit 3) or Screening (Visit 2)), then that measurement will be considered as baseline.

Note: the spot urine (Screening Visit 1) values are excluded from the baseline evaluation.

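### Two relevant deviations that define the primary Per Protocol set are missing data, which conflicts with the SAP's rule that no subject leaves the primary MMRM for missing data

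*SAP*

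**What the plan says.** SAP 3.4.1.2 fixes the primary population: change in UACR at Day 169 for each dose "compared with the pooled placebo group will be analyzed based on the Per Protocol Population". SAP 3.2 (Table 2) limits that population to Full Analysis subjects who receive dapagliflozin after Week 12 and who "do not violate the terms of the protocol in a way that may affect the primary efficacy endpoint significantly (relevant protocol deviations (IPDs", and adds: "The relevant IPDs are reported in Section 3.3.2".

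SAP 3.3.2 lists four categories of relevant deviation: eligibility, prohibited medication, missed visits and urine samples. The last two concern missing data:

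- Missed visits: "Missed visit (we allow 1 missed visit. For IA any missed Visit before Day 85 would be relevant PD". The sentence continues that this does not apply at the final analysis if the subject attends the remaining visits.
- Urine samples: "Did not provide UACR samples / samples were lost / samples were damaged". No number of samples and no visit is specified.

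SAP 3.4.1.2.3 states that the primary MMRM takes in all subjects and all data points, and then: "No subjects will be excluded because of missing data, and no imputation will be done for missing data". On incomplete triplicates, SAP 3.4.1.2.1 says: "In case of missing values for UACR the geometric mean will be calculated considering the number of the available measurements".

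**The concern.** The same event has two consequences. Under 3.2 and 3.3.2, missed visits beyond the allowance, or UACR samples that were not obtained, remove the whole subject. Under 3.4.1.2.3 the subject stays and the MMRM uses whatever was observed. Two programmers working from different sections would build different primary data sets.

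An MMRM lets incomplete subjects contribute under missing-at-random. Removing them first conditions the comparison on behaviour after randomisation. For missed visits and samples not provided, that behaviour could depend on treatment or tolerability, so bias is possible. For samples lost or damaged in handling, the cost is mainly precision.

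The plan has no specified check on this. The ANCOVA with LOCF in 3.4.5 uses the same Per Protocol Population. The Full Analysis Population is specified for a UACR model only at Week 12 (3.4.2.2), although Table 2 assigns it to all efficacy analyses.

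**Working it through.** **Step 1. Put example subjects through both sets of rules.** All are assumed to have received dapagliflozin after Week 12 and to have no other relevant deviation.

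| Subject | 3.2 with 3.3.2 | 3.4.1.2 and 3.4.1.2.3 |
|---|---|---|
| Lost to follow-up after Day 113; Days 141 and 169 missed | Two missed visits, more than the one allowed; no later samples: removed | Intercurrent event; data missing from then on, earlier data kept |
| Attends every visit; all Day 141 samples lost in transit | Samples lost: removed | Day 141 missing, every other visit used |
| Misses Day 141 only | One missed visit is allowed, but no UACR sample was provided at that visit: unclear | Kept |

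The second row does not depend on a strict reading of a single lost sample, since no value exists for that visit at all. The third row shows that the two categories also sit badly together: one missed visit is tolerated, while the urine-sample category has no matching allowance.

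**Step 2. Reproduce the plan's power.** Inputs from SAP 2.4: evaluable subjects 85 (30, 60 and 120 mg), 125 (300 mg) and 125 (placebo) after 10% dropout; 30% reduction; log-scale SD 1.0; one-sided alpha 0.05.

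- Log difference: δ = −ln(0.7) = 0.3567. The SD agrees with the stated CV: √ln(1 + 1.31²) = 1.00.
- Power = Φ(δ / √(1/n₁ + 1/n₂) − 1.645), normal approximation.
- 85 v 125: 0.3567 / √(0.01176 + 0.00800) = 2.537; Φ(0.892) = 81.4% (stated 80%).
- 125 v 125: 0.3567 / √0.01600 = 2.820; Φ(1.175) = 88.0% (stated at least 85%).

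**Step 3. Further loss f in every arm.** The noncentrality shrinks by √(1 − f). The values of f are assumptions, because the SAP gives no rate of relevant deviations.

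| Further loss | 30, 60, 120 mg | 300 mg |
|---|---|---|
| 0% | 81.4% | 88.0% |
| 5% | 79.6% | 86.5% |
| 10% | 77.7% | 84.9% |
| 20% | 73.4% | 81.0% |

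The loss that brings the smaller arms to exactly 80% solves 2.537 × √(1 − f) = 1.645 + 0.842 = 2.487, so f = 1 − (2.487/2.537)², about 3.9%.

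**Step 4. What could produce such a loss.** Assume independent misses over the six post-baseline visits in 3.4.1.2.1. The share with two or more misses is 1 − (1−p)⁶ − 6p(1−p)⁵: 3.3% at p = 5% and 11.4% at p = 10%. Both rates are assumed. Some of these subjects would already be among the 10% dropouts, or would be out of the set for not receiving dapagliflozin, so the additional loss would be smaller.

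**The case against.** The best defence is that the sections act in sequence: 3.2 and 3.3.2 fix the set, and 3.4.1.2.3 then forbids further exclusions within it. That is workable as programming. It does not remove the conflict, because the set would already have been selected on missing UACR data that 3.4.1.2, 3.4.1.2.1 and 3.4.1.2.3 say to keep and handle.

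Three further points limit the finding.

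- A reader might infer that the missed-visit category contradicts itself. It does not: it sets one rule for the interim and a more lenient one for the final analysis. The bracket is never closed, and the text leaves open whether several early misses are forgiven and whether the allowed miss may be Day 169. That is unclear drafting.
- A reader might infer that one lost or damaged sample out of a triplicate excludes a subject, and so expect large losses. The missing threshold permits that reading, but the available-sample rule goes against it. Table 2 also restricts exclusion to deviations that may significantly affect the primary endpoint, and 3.3.2 leaves details to a protocol deviation plan that is not shown. No size is claimed on that basis.
- Blinded deviations are agreed by blinded personnel before unblinding. This limits discretion but does not remove the selection.

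It is also fair that no mechanism for differential missed visits between arms is shown. Bias is a possibility here, not a demonstrated effect.

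**Conclusion.** The conflict stands. SAP 3.3.2, through Table 2, removes subjects from the primary analysis for missing visits or samples, and SAP 3.4.1.2.3 says that no subject is removed for missing data. The primary analysis set is therefore not uniquely defined.

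The effect on power is modest unless such deviations are common: about 4% further loss per arm uses up the margin above 80% for the 30, 60 and 120 mg comparisons, and 10% brings them to about 77.7%. These figures assume equal loss in all arms, the plan's SD and effect size, and no overlap with the planned dropout. The direction and size of any bias cannot be worked out from the SAP.

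A reader might also infer that correcting this restores a fully randomised comparison. It would not: receipt of dapagliflozin after Week 12 and use of prohibited medication would still select subjects after randomisation.

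**What to change.** For the final analysis, remove two categories from the relevant deviations that define the Per Protocol Population in SAP 3.3.2: the missed-visit category and "Did not provide UACR samples / samples were lost / samples were damaged". Continue to record, summarise and list both as important protocol deviations. State that missed visits are handled by the MMRM and incomplete triplicates by averaging the samples available, so that 3.3.2 agrees with 3.4.1.2.3. Bring the protocol deviation plan and the programming specification for the Per Protocol flag into line.

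The cost is a wording change, to be made before unblinding. Data collection does not change, and more subjects are retained.

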3.3.3 Demographics and Baseline Characteristics

Demographic information related to sex, age, race, weight, height, and body mass index (BMI) will be presented by treatment group and for all subjects combined. A summary of baseline disease characteristics may include duration of diabetes, specified diabetes complications, and smoking and alcohol history.

3.3.4 Study Drug Exposure

The number of doses and total dose received will be summarized for each investigational product (MEDI3506 or placebo) by descriptive statistics and frequencies.

3.3.5 Concomitant Medications

Concomitant medications will be coded using the current WHO Drug Dictionary enhanced (WHO-DD). The number and percentage of subjects who took concomitant medications for the highest anatomical therapeutic chemical (ATC) class and preferred term will be summarized by treatment for the safety analysis population. The summary of concomitant medications will include all concomitant medications taken on or after the date of first dose of investigational product or any concomitant medication started prior to first dose of investigational product that continued beyond the date of first dose of investigational product.

3.3.6 Prohibited Concomitant Medications

If a subject receives prohibited concomitant medication, which may impact their efficacy assessments, they should discontinue investigational product. A list of prohibited concomitant medications is provided in the CSP, all use of prohibited medications will be reviewed and identified prior to unblinding by the medical monitor.

For the purpose of analyses, prohibited concomitant medications and therapies will be summarized by highest ATC class and preferred term.

3.4 Efficacy Analyses

3.4.1 Primary Efficacy

3.4.1.1 Primary Efficacy Endpoint

The primary efficacy endpoint is the UACR change from baseline at Day 169 (Week 24) compared with placebo. Type of the estimate of interest is the percent change from baseline.

3.4.1.2 Primary Efficacy Analyses

The primary efficacy endpoint of change from baseline in UACR at Day 169 (Week 24) for each of the MEDI3506 treatment groups compared with the pooled placebo group will be analyzed based on the Per Protocol Population. For the intercurrent events, if a subject is lost to follow-up (EOT), discontinues treatment due to AE, or uses prohibited medication, the UACR data are treated as missing on or after the event and no imputation is performed. The primary analysis will use a mixed model repeated measures (MMRM) analysis with a restricted maximum likelihood (REML) approach without multiplicity adjustment. UACR will be log-transformed before entering the data in the MMRM analysis to alleviate the skewness of the data. The model will adjust for fixed effects of treatment, visit, and treatment-by-visit interaction, randomization stratification factors, baseline log UACR and baseline log UACR-by-visit interaction. Randomization stratification factors are with SGLT2i background or not, in Japan or rest of world.

To allow generality for the covariance structure for the repeated measures, the variance-covariance matrix will be assumed to be unstructured, i.e., purely data dependent, to model within subject errors. If the unstructured variance-covariance matrix will not fit, i.e., fail to converge, the following covariance structures will be utilized in the order of 1) heterogeneous toeplitz, 2) heterogeneous autoregressive of order 1, and 3) heterogeneous compound symmetry. The first (co)variance structure which does not have a convergence problem will be the one used for the analysis. If a structured covariance has to be used, the “sandwich” estimator of the variance covariance matrix of the fixed effects parameters will be used in order to deal with possible model misspecification of the covariance matrix. The denominator degrees of freedom will be calculated according to the Kenward-Roger method. Additionally, there will be no adjustment for multiplicity.

If none of the above models converge, the analysis will be altered to use an analysis of covariance (ANCOVA) with last observation carried forward (LOCF) imputation method implemented. Details of this analysis is provided in the [Section 3.4.5](#) for sensitivity analysis.

Additionally, all collected values of UACR will be listed.

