3.4.2.2 Secondary Efficacy Analyses

The change from baseline to Day 85 (Week 12) in UACR will be analysed similarly to that of the primary efficacy endpoint based on the Full Analysis Population with the cutoff at Day 85.

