3.4.5 Sensitivity Analyses

The primary endpoint of UACR at Day 169 post baseline time point in Per Protocol Population will be analyzed, as sensitivity analysis, using an analysis of covariance (ANCOVA) adjusting for treatment, baseline log UACR, and randomization stratification factors with last-observation-carried-forward (LOCF) imputation for missing post-baseline measurements. In case the LOCF analysis is needed, some data handling needs to be considered as follows.

Due to two treatment periods, different imputation rules need to be considered for data cut-off at day 85 and all data available beyond day 85,

- If the data at week 12 is missing, the latest respond before week 12 will be carried forward

- If the data at week 24 is missing, the latest response after week 12 will be carried forward

Should be noted that if subject does not have any data after week 12, then that subject will be excluded from the analysis in week 12-24. The data from unscheduled visits will be included together with other available data for endpoint imputation purpose.

Other sensitivity analyses may also be performed.

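### The primary Week 24 UACR analysis is run in a Per Protocol set defined largely by post-randomisation events, against the SAP's own rule that efficacy uses the Full Analysis Population

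*SAP*

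**What the plan says.** **Populations (SAP 3.2, Table 2).** The FAP is defined as "All subjects from cohorts 2 and 3 who are randomized and receive any study drug. Subjects are evaluated according to the treatment assigned at randomization". Its use is stated without exception: "The Full Analysis Population will be used for all analyses of demographic baseline characteristics and efficacy data". The PP set is the subset of the FAP "consisting of all subjects who receive the additional treatment with dapagliflozin post Week 12" and free of relevant important protocol deviations.

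**Relevant deviations (SAP 3.3.2).** There are four: "Did not meet inclusion/exclusion criteria"; prohibited medication before the end of treatment; missed visits, with one allowed; and UACR samples not provided, lost or damaged.

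**Where each set is used for UACR.**
- Primary analysis, Week 24 (3.4.1.2): "compared with the pooled placebo group will be analyzed based on the Per Protocol Population".
- Sensitivity analysis, Week 24 (3.4.5): "The primary endpoint of UACR at Day 169 post baseline time point in Per Protocol Population will be analyzed", by ANCOVA with LOCF.
- Secondary analysis, Week 12 (3.4.2.2): "based on the Full Analysis Population with the cutoff at Day 85".

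**Missing data and intercurrent events.** SAP 3.4.1.2.3 says that missing data will not cause any subject to be left out of the primary MMRM. SAP 3.4.1.2 sets UACR to missing from the day of loss to follow-up, discontinuation for an AE, or prohibited medication. Values before that day are therefore kept.

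**The concern.** Two statements about the population for the primary comparison cannot both stand, and the SAP does not rank them. The one given in the primary analysis section is the weaker choice for a superiority comparison. Randomisation makes the arms comparable at baseline. It does not make comparable the subsets who stayed long enough to add dapagliflozin, attended nearly all visits, supplied samples and avoided prohibited drugs. If AEs on active drug or worsening disease on placebo drive those events, the groups compared at Week 24 differ for reasons other than the drug's effect on UACR.

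The PP set also undercuts the model placed on it. An MMRM is useful here because it draws on the early visits of subjects who later drop out. PP removes anyone who stops before dapagliflozin, and any user of prohibited medication, together with those early visits.

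Finally, Week 12 and Week 24 UACR estimates come from different populations. This hampers the between-period albuminuria comparison in secondary objective 4.

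**Working it through.** **1. The SAP's rules side by side**

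| Situation | Rule in 3.4.1.2 / 3.4.1.2.3 | Effect of the PP definition (3.2, 3.3.2) |
|---|---|---|
| More than one missed visit, or UACR samples missing | Subject stays in the MMRM | Relevant deviation: subject removed |
| Prohibited medication | Earlier UACR data kept | Subject and all data removed |
| Stops before dapagliflozin, e.g. for an AE | Earlier UACR data kept | Subject and all data removed |
| Stays in study, never receives dapagliflozin | Not listed as an intercurrent event | Subject and all data removed |

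The first three rows are internal conflicts. The fourth is a gap: the main PP criterion has no counterpart in the intercurrent-event rule.

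**2. The stated power, reproduced (SAP 2.4)**

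Inputs: 30% reduction, δ = −ln(0.70) = 0.3567; log SD 1.0; one-sided α = 0.05; evaluable numbers 85 and 125.

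Power = Φ(δ / √(1/n₁ + 1/n₂) − 1.645)

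- 125 v 125: Φ(0.3567/0.1265 − 1.645) = 88.0%. The SAP says at least 85%.
- 85 v 125: Φ(0.3567/0.1406 − 1.645) = 81.4%. The SAP says 80%.

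The SAP's figures hold. They allow for 10% dropout and nothing else.

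**3. Lower-dose power if total loss exceeds 10%** (loss rates assumed; 95 v 140 randomised)

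| Total loss | n | Power |
|---|---|---|
| 14% | 81.7 v 120.4 | 80.0% |
| 15% | 80.75 v 119 | 79.6% |
| 20% | 76 v 112 | 77.5% |
| 25% | 71.25 v 105 | 75.1% |

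**4. Selection under no true effect: closed form** (300 mg v placebo, 140 randomised per arm)

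Let e be the share excluded in an arm, and g the amount by which excluded subjects' log change is worse than that of included subjects. Both are assumptions. The included mean is then shifted by −e·g, so

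bias = −(e_active − e_placebo)·g, and one-sided error = Φ(|bias|/SE − 1.645) when the bias favours active.

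- e = 20% v 10%, so n = 112 v 126 and SE = √(1/112 + 1/126) = 0.130. For g = 0.25, bias is −0.025 and the error 7.3%. For g = 0.5, bias is −0.05 and the error 10.4%.
- e = 30% v 10%, so n = 98 v 126 and SE = 0.135. For g = 0.25 to 0.5, the error is 10.1% to 18.3%.
- Equal e and equal g: bias 0, error 5%.

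**5. Selection under no true effect: simulation**

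Assumptions: 140 per arm, six post-baseline visits, log SD 1.0, 15-25% lost per arm. Loss depends on the last observed change in placebo (logistic slope 1) and is random in active. Within-subject correlation is 0.6 for the second row; other completer runs used values around that. Test: two-sided 10%.

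| Subjects analysed | Bias (log units) | Two-sided error |
|---|---|---|
| All subjects, all observed data | about 0 | about 10% |
| Everyone reaching Week 12, with their observed data | 0.03-0.07 | 12-15% |
| Completers only | 0.08-0.16 | 17-33% |
| Either restricted set, same selection in both arms | about 0 | about 10% |

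On the ratio scale, exp(0.03) to exp(0.07) is about 3-7%, and exp(0.08) to exp(0.16) is about 8-17%. The second row is a lower case, because visit and sample exclusions would add to it. The third is an extreme, because PP allows one missed visit and does not list AE discontinuation as a relevant deviation. If the selection acts on the active arm instead, the direction reverses.

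**The case against.** **The dapagliflozin question is legitimate.** SAP section 1 asks about the effect without and with dapagliflozin, and restricting to subjects who took it looks like a direct answer. The aim stands, but restriction is not the only way to reach it: non-receipt can be named as an intercurrent event while the randomised comparison is kept.

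**Deviations are agreed blind.** SAP 3.3.2 has blinded personnel agree the blinded deviations before unblinding. This limits reviewer bias. It does not prevent selection through events that treatment itself causes, and deviations relating to study medication or dosing are agreed by unblinded personnel.

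**A Week 24 FAP analysis may sit in hidden text.** A reader might infer that none is planned at all. The documents do not support that. Section 3.4.3 is not visible, the exploratory objectives are not shown, and SAP 3.5.2 plans Day 169 analyses in both sets for endpoints that are redacted. SAP 3.4.5 also leaves room for other sensitivity analyses, without committing to any. The supportable statement is that none is specified for UACR in the visible text.

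**The error figures could be read as a property of this trial.** They are not. The 17-33% range needs one-arm selection and PP equal to completers, and the SAP gives neither exclusion rates nor selection strength.

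**Power does not separate the two sets sharply.** Subjects who stop early have no on-treatment Week 24 value in either set, and an FAP MMRM recovers only part of that information from earlier visits. This stands. The power point is that no allowance is made for PP exclusions beyond dropout, not that the FAP restores full power.

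**The safety objective could seem affected too.** It is not. Secondary objective 2 is analysed in a single Safety Analysis Population for both data cuts (SAP 3.6).

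**Conclusion.** The concern holds. Table 2 conflicts with 3.4.1.2 and 3.4.5 on the population for the primary endpoint. The PP exclusions also conflict with the missing-data rule in 3.4.1.2.3 and discard earlier data that the intercurrent-event rule would keep. Eligibility failure is the one relevant deviation that is not a post-randomisation event; the other PP criteria are, and treatment can influence them.

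The size and direction of any bias cannot be derived from the SAP. The range runs from about zero (identical selection in both arms), through 0.03-0.07 log units, to 0.08-0.16 in the one-arm, completers-only extreme, all on assumed losses of 15-25%. Lower-dose power drops under 80% beyond about 14% total loss, which is a modest shortfall.

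This needs correcting before the final analysis because it concerns the sole primary efficacy analysis, and its specified sensitivity analysis shares the same weakness.

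**What to change.** 1. In 3.4.1.2, make the FAP the primary population at Week 24, using the MMRM as written with all UACR data from the planned Visits 4 to 9.
2. State in the estimand how non-receipt of dapagliflozin is handled as an intercurrent event, alongside loss to follow-up, AE discontinuation and prohibited medication. The existing rule does not cover it.
3. Keep the PP analysis as supportive and label it so.
4. Reconcile 3.2 (Table 2), 3.3.2, 3.4.1.2, 3.4.1.2.3 and 3.4.5, so that population, deviation and missing-data rules agree.

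Week 12 and Week 24 would then rest on the same population. Reporting the difference between them from one model is optional.

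The cost is SAP wording and a population flag; no new data are needed. The Week 24 estimate may be slightly attenuated by subjects who never added dapagliflozin, and the supportive PP analysis would show by how much the two differ.
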